6.1. General considerations for efficacy endpoints

All efficacy analyses will be performed on the scheduled visits/study weeks for the ITT population. For NPRS and DSIS, the visit refers to study week.

The primary hypothesis is to test if there is a greater mean reduction from baseline in NPRS pain intensity for the RTA 901-treated groups compared with placebo after 12 weeks of double-blind treatment.

Stratification factor (standard of care) will not be included for any modelling due to <10 patients of randomized patients taking duloxetine at randomization.

6.2. Multiplicity Control

A sequential stepwise testing will be performed on the primary endpoint for RTA 901 group (80mg, 10mg) compared to placebo in the following testing order to control the overall type I error at two-sided alpha level of 0.05:

- Step 1: Comparison of 80 mg group versus placebo group. If p-value <0.05, then proceed to Step 2. If not, testing for subsequent step is considered as exploratory.
- Step 2: Comparison of 10 mg group versus placebo group.

No formal testing will be performed for the secondary endpoints.

6.3. Primary endpoint of change from baseline in NPRS average pain intensity at week 12

The primary endpoint is the change from baseline in the average daily NPRS pain intensity score during Week 12.

The NPRS of pain intensity is a numeric scale, ranging from 0 (representing no pain at all) to 10 (representing the worst pain imaginable). The subject selects a whole number (0 to 10) that best indicates the intensity of their neuropathic pain in the past 24 hours. Subjects will report how they perceive their average neuropathic pain intensity during the past 24 hours at bedtime.

The weekly mean is defined as the sum of non-missing daily scores divided by the number of days with non-missing scores for that week. Subjects with fewer than 3 daily scores during an analysis week will be considered to have a missing weekly average for that week.

No imputation will be conducted at weekly mean level.

The MMRM model will include baseline NPRS score, visit, treatment, the interaction of treatment and visit, the interaction of baseline NPRS score and visit. The analysis visit will include all visits (study week) up to week 12 during double-blinded treatment period. An unstructured covariance (UN) matrix will be used to model the within-subject variability. Model convergence will be checked. If the unstructured covariance model fails to converge with the Newton-Raphson algorithm after increasing the default maximum iterations, the Fisher scoring algorithm will be used to provide initial values of the covariance parameters.

If the model does not converge with an unstructured covariance matrix, then the analysis visit will include weeks 1, 2, 4, 6, 8, 10 and 12 per protocol scheduled assessment visits.

In the event that none of the above methods yield convergence, the following covariance structures are substituted, in the order listed. Each subsequent covariance structure is used only if each previous covariance structure is used, and no previous model converged.

- 1. Heterogeneous Toeplitz covariance structure (assuming different variances at each time point and that measurements taken closer together in time are more highly correlated than those taken farther apart).
- 2. Toeplitz covariance structure (assuming measurements taken closer together in time are more highly correlated than those taken farther apart).
- 3. First order auto-regressive [AR(1)] covariance structure (assuming measurements taken closer together in time are more highly correlated than those taken farther apart, but the correlation is more constrained than the Toeplitz structure).
- Compound symmetry covariance structure (assuming equal correlation for measurements from a patient, regardless of how far apart in time they were taken). A compound symmetry covariance structure was assumed in the sample size calculation.

The corresponding plots will also be generated. The primary inference will be based on the treatment comparison at Week 12. The LS means with standard errors of each dose level at each visit as well as of treatment differences between the RTA 901 group (10 mg, 80 mg) vs. placebo at each visit will be presented, along with 95% CI and p-value at each visit.

Descriptive statistics for observed data, including NPRS score and change from baseline in the NPRS weekly average scores, will be evaluated by treatment group and visit (including EOS visit) with descriptive statistics (mean, SD, median, 1st and 3rd quartiles, range) in the ITT population.

The change from baseline of weekly average NPRS score will also be analyzed for the perprotocol population using the same MMRM model as for the ITT population as a sensitivity analysis.

A sensitivity analysis will be performed excluding any data after a subject discontinued randomized study treatment.

Product: RTA 901 (BIIB143) Statistical Analysis Plan Study: 901-C-2102 Version: 1.0

An MMRM model including all post-randomization visits up to Week 16 will be performed as sensitivity analysis.

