### 8. STATISTICS

### 8.1. Sample Size Estimate

This study will be conducted in 2 parts. A total of approximately 192 subjects (64 subjects per treatment arm) are planned for randomization in Part 1 and approximately 192 subjects (64 subjects per treatment arm) are planned for randomization in Part 2, for a total of 384 subjects to be randomized. This sample size is based on a dose-ranging scheme to evaluate initial safety, efficacy, of RTA 901 in this population. The primary comparisons for efficacy are between each of the 2 RTA 901 treatment groups and the placebo treatment group. The overall Type I error rate will be controlled at the 0.05 significance level. A hierarchical testing strategy to control the overall Type I error will be defined in the SAP. Power calculations are based on a 2-sample t-test with no adjustments for multiple comparisons. The study assumes a difference in NPRS pain intensity means of 1.2 between each RTA 901 treatment group and the placebo treatment group and a standard deviation of 2.4.

If doses selected for Part 2 do not include doses studied in Part 1, then an analysis by dose group for Part 1 or Part 2 doses will be performed following completion of each study part. Within each Part, with 64 subjects per treatment group, each study part has 80% power to compare treatment groups to placebo.

If doses selected for Part 2 include any doses studied in Part 1 (ie, 10 or 80 mg), then an analysis by dose group will be performed using Part 1 and Part 2 combined, following completion of the study. The dose group that is enrolled in both parts will have 128 subjects. With 128 placebo subjects compared to 128 subjects in the RTA 901 dose group, there is 98% power to detect the same difference (1.2 NPRS points) assuming the same standard deviation (2.4). RTA 901 dose groups that are enrolled in only 1 part will have 64 subjects. With 128 placebo subjects compared to 64 subjects in each RTA 901 dose group, there is 90% power to detect the same difference (1.2 NPRS points) assuming the same standard deviation (2.4).

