2.2. Study Design

Study 901-C-2101 is a 2-part, randomized, placebo-controlled, double-blind, Phase 2 study to evaluate the safety, tolerability, efficacy, of RTA 901 in qualified subjects with DPNP.

Part 1 of the study includes screening period of up to 2 weeks, a run-in period of 2 weeks, a treatment period of 12 weeks and a safety follow-up period of 4 weeks (see Figure 1). Approximately 192 subjects in Part 1 who remain eligible (according to Randomization eligibility criteria) will be randomized 1:1:1 to either RTA 901 (10 or 80 mg) or placebo at Day 1 and stratified by SOC pain medication (duloxetine or pregabalin/gabapentin).

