2.4. Sample Size Considerations

This sample size for Part 1 is based on a dose-ranging scheme to evaluate initial safety, efficacy, of RTA 901 in patients with DPNP. The primary comparisons for efficacy are between each of the 2 RTA 901 treatment groups and the placebo treatment group. With assumed treatment difference of 1.2 and standard deviation of 2.4 in NPRS pain intensity, 64 subjects per arm approximately provides 80% power with two-sided alpha of 0.05. The purpose of Part 1 is to provide dose selection information for Part 2.

3. Definitions

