6.4.5. Change from baseline in the DSIS

The DSIS is a numeric scale, ranging from 0 representing no interference with sleep to 10 representing complete inability to sleep. The subject selects a whole number (0 to 10) that best indicates his/her ability to sleep in the past 24 hours. The DSIS will be completed daily by subjects upon waking (3-minute self-administered questionnaire).

The weekly mean is defined as the sum of non-missing daily scores divided by the number of days with non-missing scores for that week. Subjects with fewer than 3 daily scores during an analysis week will be considered to have a missing weekly average for that week.

[figure not shown]
No imputation will be conducted at weekly average level.

Descriptive statistics for observed data, including actual value and change from baseline in weekly average DSIS score, will be evaluated by treatment group and visit (including EOS visit) with descriptive statistics (mean, SD, median, 1st and 3rd quartiles, range) in the ITT population.

Change from baseline in weekly DSIS average score will be analyzed through MMRM model. The MMRM model will include baseline DSIS score, visit, treatment, the interaction of treatment and visit, the interaction of baseline DSIS score and visit. Unstructured covariance will be used. All analysis visits up to Week 12 will be utilized. In the event that convergence issue occurs, similar subsequent steps will follow described in section 6.3

LS means and treatment differences will be presented with 95% confidence intervals, standard errors, p-values at each visit. A line plot of LS mean changes from baseline over time will also be provided.

A sensitivity analysis will be performed excluding any data after a subject discontinued randomized study treatment.

Product: RTA 901 (BIIB143)

Study: 901-C-2102 Version: 1.0

Statistical Analysis Plan

Product: RTA 901 (BIIB143)

Study: 901-C-2102 Version: 1.0

Statistical Analysis Plan

Product: RTA 901 (BIIB143) Statistical Analysis Plan Study: 901-C-2102 Version: 1.0

7. Safety endpoints

All analyses of the safety data are performed using the safety analysis set. Descriptive statistics are presented by treatment group actually received in the safety analysis set. No statistical testing will be performed on the safety data.

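### The last three covariance fallbacks in SAP 6.3 assume one variance for all weeks and no robust standard error is specified; the main analysis is unaffected, but the contingency should be made safe

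*SAP*

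**What the plan says.** SAP 6.3 fits the primary MMRM with an unstructured covariance over all 12 weeks. If that fails, Fisher scoring supplies starting values. If it still fails, the unstructured model is refitted on Weeks 1, 2, 4, 6, 8, 10 and 12. After that: "In the event that none of the above methods yield convergence, the following covariance structures are substituted, in the order listed". The order is heterogeneous Toeplitz, Toeplitz, AR(1) and last "Compound symmetry covariance structure (assuming equal correlation for measurements from a patient, regardless of how far apart in time they were taken". Each is used only if everything before it failed.

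Primary inference is the Week 12 contrast, reported with standard errors, a 95% CI and a p-value. The SAP names neither a standard error estimator nor a degrees-of-freedom method. SAP 6.2 tests 80 mg and then 10 mg "to control the overall type I error at two-sided alpha level of 0.05". SAP 6.4.5 carries the chain over to the sleep score: "In the event that convergence issue occurs, similar subsequent steps will follow described in section 6.3".

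**The concern.** Toeplitz, AR(1) and compound symmetry each estimate a single variance from all weeks. A model-based standard error for Week 12 then reflects the average spread over the treatment period, not the spread at Week 12. If scores spread out over time, that standard error is too small, and the p-value, the CI and the step from 80 mg to 10 mg are anti-conservative. Under the global null, the familywise error of a fixed sequence equals the step 1 rate, so any inflation passes straight through.

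A rise in spread is plausible on the SAP's own premise. Its descriptions of the first three structures assume that correlation weakens with time apart, and the model adjusts for baseline by visit. If the raw-score variance is constant, the residual variance at week k is proportional to 1 − ρ_k², where ρ_k is the correlation with baseline. This grows as ρ_k falls.

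A fallback list exists to remove discretion. Repairing it after a convergence failure would look post hoc.

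**Working it through.** **Inputs from the documents.** Two-sided alpha 0.05 (SAP 6.2). Allocation: subjects "will be randomized 1:1:1 to either RTA 901 (10 or 80 mg) or placebo" (SAP 2.2). SAP 2.4: "With assumed treatment difference of 1.2 and standard deviation of 2.4 in NPRS pain intensity, 64 subjects per arm approximately provides 80% power".

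**Inputs assumed.** The SD by week, the correlation pattern and the dropout are not given in the current text. I set the Week 12 SD at 2.4 and vary the Week 12/Week 1 SD ratio.

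**The plan's own figure.** True standard error of the Week 12 difference: 2.4 × √(2/64) = 0.424. Then 1.2/0.424 = 2.83 and Φ(2.83 − 1.96) = 0.807 (0.801 with the noncentral t). The stated 80% is reproduced.

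**Formula.** Let R be the model-based SE divided by the true SE at Week 12. The large-sample two-sided type I error is 2[1 − Φ(1.96 R)]. For compound symmetry with complete data, the fitted variance is the mean of the weekly variances, so R = √(mean variance / 2.4²).

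**Compound symmetry, 12 weeks, complete data, SD rising linearly to 2.4:**

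| SD ratio | Week 1 SD | Mean variance | R | Type I error |
|---|---|---|---|---|
| 1.0 | 2.4 | 5.76 | 1.000 | 5.0% |
| 1.2 | 2.0 | 4.86 | 0.918 | 7.2% |
| 1.5 | 1.6 | 4.06 | 0.840 | 10.0% |
| 2.0 | 1.2 | 3.38 | 0.766 | 13.3% |

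At ratio 1.5 the reported SE would be about 0.424 × 0.840 = 0.356. On the 7 scheduled visits, R is 0.913, 0.831 and 0.754 for ratios 1.2, 1.5 and 2.0, giving 7.4%, 10.4% and 14.0%.

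**Wider range.** The same limit was computed for Toeplitz, AR(1) and compound symmetry, on 12 or 7 visits, with three correlation patterns and 0% or 20% completely random dropout:

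| Pattern of SD over weeks | Type I error |
|---|---|
| Constant | 4.6-6.2% |
| Linear rise, ratio 1.2 | 6.9-8.6% |
| Linear rise, ratio 1.5 | 9.8-11.9% |
| Linear rise, ratio 2.0 | 12.8-16.0% |

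Two other shapes were run for a single correlation pattern. With a rise to Week 4 and then a plateau, ratios 1.2 to 3.0 gave 5.7-9.4%. With a falling SD (ratio 0.8) the error was 2.3-3.1%.

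A simulation of the compound symmetry REML fit (3 × 64 subjects, 20% dropout, 1,500 trials per case) gave 5.5%, 6.8%, 11.1% and 15.4% for ratios 1.0, 1.2, 1.5 and 2.0.

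**What the SAP's correlation premise would imply.** Suppose the correlation with baseline falls linearly from 0.8 to 0.6 (assumed). For 12 weeks the mean of 1 − ρ² is 0.506, against 0.64 at Week 12. So R = √(0.506/0.64) = 0.889, and the error is 8.1%. A fall from 0.9 to 0.6 gives 10.9%.

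**Does the robust standard error repair it?** Simulation on 7 visits with 12% random dropout, 1,500 trials per case:

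| SD path | Structure | Model-based SE | Sandwich SE |
|---|---|---|---|
| 1.8 to 2.4 | CS | 9.6% | 5.1% |
| 1.8 to 2.4 | AR(1) | 8.5% | 4.8% |
| 1.2 to 2.4 | CS | 16.2% | 5.3% |
| 1.2 to 2.4 | AR(1) | 12.9% | 5.0% |

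**The case against.** **The chain will almost certainly not get that far.** This stands. In 1,000 simulated trials with 3 × 64 subjects, SD rising from 1.2 or 1.8 to 2.4, and 12% or 25% dropout (some runs with 5% intermittent missing weeks), the unstructured 12-week model converged every time, in at most 8 iterations where this was recorded. Those were Gaussian data fitted outside SAS, so real diary data could behave worse, but the unconditional effect on the error rate is close to zero.

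**A reader might infer that the plan doubles or triples its false-positive rate.** The documents do not support that. They give one SD, 2.4, and none by week. A 10% error needs R = 0.839, so a mean variance about 70% of the Week 12 variance. A 15% error needs R = 0.734, or about 54%. With linear growth, that means SD ratios of about 1.5 and about 1.9-2.6. The opposite inference is no better supported. The SAP remarks that "A compound symmetry covariance structure was assumed in the sample size calculation", which would imply a constant SD, but this is a planning assumption without data. Protocol 8.1 moreover says "Power calculations are based on a 2-sample t-test with no adjustments for multiple comparisons".

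**Model-based standard errors are inferred.** The SAP is silent on the estimator. That is correct, and the silence is the gap to close.

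**The consequences are limited.** SAP 6.2 plans no formal testing of secondary endpoints, so for the sleep score only descriptive CIs and p-values are affected. Part 2 doses come from a separate exposure-response analysis (Protocol 3.6), not from this p-value.

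**Conclusion.** The point holds as a weakness in a contingency, not as a flaw in the main analysis. Fallbacks 2-4 pool the variance over weeks, inference is at Week 12, and no robust standard error is specified.

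The size is conditional on three things: all earlier steps failing, model-based standard errors being used, and the SD rising over weeks. Given those and a linear rise, the nominal 5% becomes about 7-9%, 10-12% or 13-16% for SD ratios of 1.2, 1.5 or 2.0. With a constant SD there is essentially no problem, and with a falling SD the test is conservative. Nothing in the documents shows which pattern will occur. Priority: low.

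**What to change.** Add to SAP 6.3, and by reference to 6.4.5: *For any covariance structure other than unstructured, standard errors will use the empirical (sandwich) estimator.* Alternatively, replace items 2-4 with heterogeneous-variance versions (ARH(1), heterogeneous compound symmetry). Either one addresses the variance problem.

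The same edit could state whether the structured fallbacks use 12 weeks or 7 visits. The 7 are unequally spaced, which Toeplitz and AR(1) by visit order ignore.

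The cost is one sentence and one software option. The downsides are a slight small-sample bias of the sandwich estimator at about 64 per arm and the loss of some degrees-of-freedom adjustments. The sandwich also corrects only the standard error. If dropout depends on earlier scores, a wrong covariance can bias the Week 12 estimate itself, and the simulations above covered random dropout only.

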6.4. Secondary efficacy endpoints

6.4.1. ≥30% responder (yes/no) in NPRS average pain intensity at Week 12

The proportion of subjects who had ≥30% neuropathic pain reduction response, defined as a ≥30% reduction from baseline in the NPRS average pain intensity score at Week 12, will be analyzed with logistic regression using terms for treatment and baseline NPRS score. The odds ratio, its 95% CI and the p-value for RTA901 doses compared to placebo will be presented. Subject with missing weekly mean at Week 12 will be classified as non-responder.

The proportion of subjects who had $\geq 30\%$ neuropathic pain reduction at each week will be summarized by visit and treatment group. For each visit, subjects with missing weekly mean will be classified as non-responder at the corresponding visit. A line plot of proportions for responders will also be presented by visit and treatment group.

6.4.2. ≥50% responder (yes/no) in NPRS average pain intensity at Week 12

The proportion of subjects who had ≥50% neuropathic pain reduction from baseline in the NPRS average pain intensity at Week 12 compared to baseline will be analyzed in a similar way as the 30% neuropathic pain reduction response in section 6.4.1.

The proportion of subjects who had ≥50% neuropathic pain reduction at each week will be summarized by visit and treatment group. For each visit, subjects with missing weekly mean will be classified as non-responder at the corresponding visit.

A line plot will also be presented by visit and treatment group.

Responder curve of the proportion of subjects achieving various level of percentage reduction thresholds from baseline in the weekly average neuropathic pain score at Week 12 will be generated in 1% increments from 0 to 100% by treatment group. Subjects will be considered to have reached the percentage threshold if they had a reduction (improvement) equal to or greater than a certain threshold in the weekly average neuropathic pain score at Week 12. Subjects with a missing weekly mean NPRS score at Week 12 will be classified as non-responder.

6.4.3. Proportion of rescue medication use

If rescue medication is needed, subjects will be instructed to take acetaminophen 500 mg every 4 to 6 hours as needed (not to exceed 3000 mg per day), ibuprofen 200 to 400 mg every 4 to 6 hours as needed not to exceed 1200 mg daily (protocol version 3.0), or ibuprofen 200 to 400 mg every 4 to 6 hours as needed (not to exceed 600 mg/day) for up to 3 days in a 7-day period (not calendar week) (protocol version 4.0).

The rescue medications are recorded daily at bedtime in the e-diary. The number and percentage of subjects who used any rescue medication during the 12-week treatment period will be summarized by treatment group and study week.

A logistic regression model will be performed on proportion of rescue medication use at Week 12 including baseline NPRS score and treatment. The odds ratio, its 95% CI and the p-value for RTA901 doses compared to placebo will be presented.

6.4.4. Quantity and timing of rescue medication use

The amount of rescue medication used per day during the 12-week treatment period will be calculated as the total dosage recorded divided by total days of study drug exposure during the treatment period. The rescue medication used per day will be summarized using the mean, standard deviation, minimum, median and maximum by treatment group. Rank ANCOVA will be performed by category of rescues medication use (Acetaminophen, NSAIDs). The model will include rank of baseline NPRS and treatment group. P-value for the comparisons of RTA 901 group (10mg, 80mg) vs placebo will be presented.

Time to first occurrence of rescue medication use will be calculated for each patient during double-blinded treatment period. If subject had an event, the day of the event will be date of the first date of rescue medication use recorded in e-diary during the treatment period. If a subject withdraws from the study prior to Week 12 and the subject did not take any rescue medication, then the subject will be censored on the last day they were in the study. The start date for time to first occurrent of rescue medication use is defined as the date of the first randomized dose. The proportion of first occurrence of rescue medication use will be estimated using the Kaplan-Meier (KM) product limit method and be presented as KM curves over time. The KM estimates of median time to first occurrence of rescue medication use, percentiles (5th,10th,25th, 50th and 75th) and associated 95% confidence limits will be presented. P-value from log-rank test will be presented.

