# 3.5. Follow-up/End of Study (Week 16)

The Follow-up Period includes 1 clinic visit on Day  $113 \pm 2$ , which must occur approximately 4 weeks following the EOT visit. Procedures will be performed according to the Schedule of Assessments (Table 4). Completion of this visit concludes the subject's participation in the study.

Subjects will be directed to continue completing the NPRS and recording their rescue medication usage in the e-diary at bedtime. Upon waking, subjects will be asked to complete the DSIS.

Additional procedures are to be completed according to the Schedule of Assessments (Table 4).

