## 4.6. Study Drug Discontinuation, Interruption, and Subject Termination

## 4.6.1. Discontinuation of Study Drug

Discontinuation from study drug does not mean discontinuation from the study. Subjects who discontinue the study drug early for any reason should complete the procedures associated with the Week 12/EOT visit at the closest study visit. If the subject discontinued study drug during a study visit, the EOT procedures should be performed during that study visit. If the subject discontinues study drug in between visits, he/she will perform the EOT procedures at the next scheduled study visit. The subject will then complete the procedures associated with the Week 16/end of study (EOS) visit 4 weeks after discontinuation.

If a clinically significant (CS) finding is identified (including, but not limited to changes from baseline) after enrollment, the Investigator or qualified designee will determine if any change in subject management is needed. Any new clinically relevant finding will be reported as an AE.

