## **5.1.7. Electronic Diary Set-up**

During Screening, subjects deemed likely to be eligible for the study will be given access to an e-diary and trained on how to record daily pain scores from Screening up to Day 1. The results will be reviewed on Day 1 to confirm that the subject is eligible for the study. The use of an e-diary will improve consistency and reliability of scoring for NPRS and DSIS, and timing of dosing and rescue medication.

Subjects will be instructed to report the NPRS number that best indicates the average intensity of pain over the last 24 hours throughout the study daily at bedtime. Subjects will also complete the DSIS via their e-diary daily upon waking. Non-compliance is defined as recording less than 70% of expected PROs during any evaluation period (visit to visit).

, treatment administration, and rescue medication usage will also be recorded in the e-diary.

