3.1.3. Analysis Visit Windows

Data from early termination visits and unscheduled visits will be assigned to an appropriate scheduled postbaseline visit using a windowing scheme for assessments that are tabulated or summarized by visit. Scheduled visits will not be windowed.

Numeric pain rating scale (NPRS) and daily sleep interference scale (DSIS) are collected daily using an e-diary form. The daily scores will be mapped to an analysis "Week" according to the following windows defined by Study Day in conjunction with study phases described above. Subjects are instructed to report the NPRS number that best indicates the average intensity of neuropathic pain over the last 24 hours throughout the study daily at bedtime. Subjects also complete the DSIS via their e-diary daily upon waking.

The weekly mean is defined as the sum of non-missing daily scores divided by the number of days with non-missing scores for that week. Subjects with fewer than 3 daily scores during an analysis week will be considered to have a missing weekly mean for that week.

The analysis window for efficacy endpoints will be defined based on the schematic as follows:

Table 2: Analysis Visit Window for weekly NPRS average pain intensity

Visit	Lower Bound in Study Day (inclusive)	Upper Bound in Study Day (inclusive)
Run-in period	First record during run-in period	-1
Randomized/treatm	ent period	
Baseline	-7	-1
Week 1	1	7
Week 2	8	14
Week 3	15	21
Week 4	22	28
Week 5	29	35
Week 6	36	42
Week 7	43	49
Week 8	50	56

Week 9	57	63				
Week 10	64	70				
Week 11	71	77				
Week 12 (EOT)	78	84				
Follow-up period						
Week 13	85	91				
Week 14	92	98				
Week 15	99	105				
Week 16 (EOS)	106	112				
Week 16 (EOS)	106	112				

Note1: the NPRS number that best indicates the average intensity of neuropathic pain over the last 24 hours throughout the study daily at bedtime, recorded using e-dairy.

Note 2: Run-in visit is intended to describe run-in phase average pain score prior to first dosing in randomized phase.

Note 3: All available data will be used to calculate the weekly average mean up to Week 12 regardless of treatment discontinuation per ITT principle.

Note 4: If the last study dose for a patient is beyond the defined windowing for Week 12, only off study treatment days will be used to calculate off study treatment follow-up weekly mean.

Table 3: Analysis Visit Window for DSIS

Visit	Lower Bound in Study Day (inclusive)	Upper Bound in Study Day (inclusive)			

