5.5. Study Treatment Exposure

The duration of study drug exposure will be based on the number of days on treatment from the first randomized dose of study drug until the last randomized dose of study drug (last dose – first dose + 1). The first dose should be administrated in clinic and recorded on the Day 1 dosing form. The last dose should be recorded on the end of treatment form.

The number and percentage of subjects in each of the following cumulative duration of exposure categories will be summarized weekly up to Week 12. In addition, days of exposure to the study drug will be summarized as a continuous variable with summary statistics by treatment group and overall.

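### Rescue medication per day (SAP 6.4.4) counts dose over the treatment period but days only to the last dose, with no rule for missed diary days, so the arm means can partly reflect drug stopping and diary completion

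*SAP*

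**What the plan says.** Protocol 2.2.2 lists the quantity of rescue medication used during the Treatment Period as part of a secondary endpoint. SAP 6.4.4 turns it into an amount per day over the 12-week treatment period, "calculated as the total dosage recorded divided by total days of study drug exposure during the treatment period". It reports mean, SD, minimum, median and maximum by arm, and p-values from a rank ANCOVA within each rescue category.

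SAP 5.5 counts exposure "from the first randomized dose of study drug until the last randomized dose of study drug", that is, last dose minus first dose plus 1. SAP 3.3.3 gives the Treatment Period a different end, namely Week 12/EOT.

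Stopping drug is not leaving the study (Protocol 4.6.1). A subject who stops during a visit has the EOT procedures at that visit. Otherwise: "If the subject discontinues study drug in between visits, he/she will perform the EOT procedures at the next scheduled study visit". Then: "The subject will then complete the procedures associated with the Week 16/end of study (EOS) visit 4 weeks after discontinuation". Protocol 3.5 keeps the diary going during follow-up: "Subjects will be directed to continue completing the NPRS and recording their rescue medication usage in the e-diary at bedtime".

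On the data source, SAP 6.4.3 says: "The rescue medications are recorded daily at bedtime in the e-diary". For NPRS and DSIS, SAP 3.1.3 sets the weekly mean as the "sum of non-missing daily scores divided by the number of days with non-missing scores for that week". Notes under the SAP visit-window tables keep NPRS and DSIS data to Week 12 whether or not the subject is still on drug. The visible text has no matching rule for rescue.

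**The concern.** A rate needs the same days above and below the line. Here they can differ in two ways that work in opposite directions.

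- **After the last dose.** The subject is off drug but, until the early EOT visit, arguably still in the treatment period and still recording rescue. Those doses can be counted while the days are not, so the rate goes up.
- **Before the last dose.** A day without a diary entry adds nothing to the dose total but remains an exposure day. The rate goes down, as if no rescue had been taken.

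If arms differ in early stopping or in diary completion, their mean rescue use can differ when true use does not. Readers use rescue quantity to interpret the pain scores, so a shift from this source could mislead. The section also leaves open where counting stops for an early stopper, and that choice is better made before unblinding.

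**Working it through.** The plan gives no figure for this endpoint, so there is none to reproduce. The figures below show how far the formula departs from a matched-days rate when daily use is constant.

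**Inputs from the documents.** Post-baseline treatment visits at Days 8, 15, 29, 43, 57, 71 and 85 (schedule of assessments; the ±2-day windows are ignored). Exposure = last dose − first dose + 1 (SAP 5.5). EOT at the same or next scheduled visit (Protocol 4.6.1).

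**Inputs assumed.** Early-stopping rates, diary completion rates, constant daily use, and last-dose days weighted equally.

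**1. Off-drug rescue, one subject.** With last dose on Day d and counting to the EOT visit:

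factor = (first visit day on or after d) / d

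| Last dose | EOT | Factor |
|---|---|---|
| Day 16 | Day 29 | 29/16 = 1.81 |
| Day 28 | Day 29 | 29/28 = 1.04 |
| Day 84 | Day 85 | 85/84 = 1.01 |

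Over d = 2 to 84 the median is 1.145 and the mean 1.249; 28% of days exceed 1.25 and 11% exceed 1.5. The maximum, 8/2 = 4.0, needs a stop on Day 2. Over d = 8 to 84 the mean is 1.18 and the maximum 1.81. If counting stops at the last dose, the factor is 1.0 throughout.

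**2. Off-drug rescue, arm means.** With no true difference, mean factor f and stopping proportions p0 and p1:

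ratio = [1 + p1(f − 1)] / [1 + p0(f − 1)]

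- 10% vs 25%, f = 1.249: 1.062/1.025 = 1.04
- 10% vs 25%, f = 1.18: 1.045/1.018 = 1.03
- 10% vs 15%, f = 1.18: 1.027/1.018 = 1.01
- equal stopping: 1.00

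**3. Missed diary days.** If use is the same on missed days, the computed rate is true use × the fraction of days completed. At 500 mg/day over 84 exposure days with 59 entries (70%), the formula gives 500 × 59/84 = 351 mg/day; dividing by diary days gives 500. Between arms, 85% vs 95% completion gives 0.85/0.95 = 0.89.

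Protocol 5.1.7 flags patient-reported outcome completion only below 70%. If that limit carried over to rescue entries, an unflagged subject could be understated by up to 1 − 0.70 = 30%.

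**4. Rank ANCOVA.** Simulated with 64 per arm and no true effect: lognormal dose (median 400 mg, log-SD 1, capped at 3000 mg), 20% or 40% users, 10% vs 30% stopping, 4000 runs (Monte Carlo standard error about 0.35 points).

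- Counting to the EOT visit: rejection 5.0% with the SAP ratio and 5.0% with matched days (20% users); 5.3% and 5.3% (40% users).
- Adding 95% vs 85% diary completion: 4.9% (20% users), 5.3% (40%) and 6.3% (80%).

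The p-value is little affected unless most subjects use rescue.

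**The case against.** **Counting may stop at the last dose.** On that reading the off-drug effect vanishes. It is a possible reading, but SAP 6.4.4 names the 12-week treatment period and SAP 3.3.3 ends that at Week 12/EOT. The reading needs to be written down. It would not help with missed diary days.

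**A reader might infer a doubling or tripling.** Counting all 28 days of off-drug follow-up gives 56/28 = 2.0 for a last dose on Day 28 and 42/14 = 3.0 for Day 14. The documents do not support this as the plan's meaning. The endpoint is tied to the Treatment Period, the text on continued recording sits under Follow-up, and the SAP separates off-treatment follow-up weeks for NPRS and DSIS. The note that keeps data to Week 12 regardless of discontinuation governs those two scales, not rescue. The factor of 4.0 belongs to a stop within the first days and is not typical.

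**The shift is small against chance.** Under the dose assumptions above with 40% users, chance alone gives a 95% range of about 0.49 to 2.09 for the ratio of arm means, so 1.03 to 1.04 would not be visible. SAP 6.4.4 also reports the median, and SAP 6.2 excludes formal testing of secondary endpoints. This stands and sets the priority.

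**The diary may not be the only source.** SAP 6.4.4 says only that the dosage is recorded. Concomitant medications go on eCRFs with dose and duration, and SAP 5.7 lists rescue as one of their categories. Whether those records fill diary gaps is not stated. The e-diary is the likelier source, but the understatement is conditional on it. The 70% limit was set for patient-reported outcomes, so the 30% figure is borrowed. The content of the SAP appendices is not visible, so a derivation rule there cannot be excluded.

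**Conclusion.** The concern holds as a minor point. As written, the formula can count rescue taken after the last dose without the days on which it was taken. If the e-diary supplies the dosage, it also treats on-drug days without an entry as days of no use.

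Under the assumed rates, the arm-mean ratio moves by about 3% to 4% from early stopping and by about 11% from diary completion, in opposite directions that need not cancel. Both disappear if stopping and completion are equal across arms, although the level in each arm would still be off. Completers with full diaries are unaffected.

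A reader might infer that the rank ANCOVA is invalid or that the efficacy conclusions are at risk. Neither follows: simulated rejection rates stay close to 5% in most settings (6.3% at the highest), and the primary analysis does not use this variable. What is exposed is the reported mean rescue dose per day in each arm.

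**What to change.** In SAP 6.4.4, apply one day-inclusion rule to both parts of the ratio.

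- **Main version.** Sum rescue dose over Day 1 to Day 84 regardless of treatment discontinuation, as for NPRS, and divide by the days in that window with a completed bedtime diary entry.
- **If the rescue item cannot record that none was taken.** Use only days with a bedtime NPRS entry, for both dose and days. Do not add a day merely because rescue was recorded on it; such days would enter only when use was positive and would bias the rate upward.
- **Sensitivity version.** Limit both parts to Day 1 through the last dose, in line with the on-treatment sensitivity analysis that SAP 6.4.5 plans for DSIS.
- **Reporting.** Give completed diary days by arm, and state whether the dosage comes from the e-diary alone.

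The cost is SAP wording and programming; the daily entries are already collected. There is one small downside: dividing by completed days assumes use is similar on missed days. If subjects skip entries when pain-free, the rate will be somewhat overstated, and the diary-day counts help a reader judge that.
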